Subjects will remain on standard of care asthma therapy throughout the study. Asthma medications may be adjusted at any time during the study at the discretion of the investigator. All changes in asthma therapy will be captured in the source documents and the electronic case report form (eCRF). At each clinic visit, adverse events will be assessed and subjects will be questioned regarding the occurrence of any exacerbations since their last clinic visit. The Asthma Control Questionnaire-5 (ACQ-5) will be performed every 12 weeks during the study and at the Exit/Early Withdrawal Visit to assist the investigator in monitoring the subject's asthma status along with spirometry assessments every 6 months and at the Exit/Early Withdrawal Visit.

Safety labs (hematology, chemistry, and liver analytes) will be drawn at Visit 1 and then approximately every 6 months thereafter. Hematology and chemistry labs will also be obtained 4 weeks after the subject's last dose of mepolizumab. Serum samples for anti-mepolizumab antibody measurements will also be obtained from subjects at baseline (Visit 1), Weeks 48, 96, 144 and at the Exit Visit/Early Withdrawal Visit. Any serum sample testing positive for anti-mepolizumab antibody will also be tested for neutralizing antibody. Subjects discontinuing mepolizumab treatment will be monitored for exacerbation of their asthma during the subsequent 4 weeks after their last dose.

Study Endpoints/Assessments

Primary Endpoints

- Annualized rate of exacerbations
- Frequency of adverse events

Secondary Endpoints

- Asthma Control Questionnaire-5 score
- Forced expiratory volume in 1 second (FEV₁)
- Number of withdrawals due to lack of efficacy
- Number of withdrawals due to adverse events
- Number of hospitalizations due to adverse events including asthma exacerbations
- Frequency of both systemic (i.e., allergic and non-allergic) and local site reactions
- 12-lead ECG parameters
- Vital signs
- Frequency of positive anti-mepolizumab binding antibodies/neutralizing antibodies
- Clinical Laboratory Parameters

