### 7.2. Adverse Events Analyses

Adverse events analyses including the analysis of adverse events (AEs), Serious (SAEs) and other significant AEs will be based on GSK Core Data Standards.

AEs occurring during pre-treatment, on-treatment and post-treatment phase will be summarised separately. Adverse events will be coded using the latest version of the Medical Dictionary for Regulatory Activities (MedDRA).

The number and percentage of subjects experiencing at least one AE will be summarised. Exposure adjusted rates of AEs will also be presented to account for the length of exposure within the trial. For the definition of exposure adjusted AEs, see Appendix 5: Derived and Transformed Data.

The details of the planned displays are provided in Appendix 10: List of Data Displays.

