### 7.5.1. Immunogenicity

Immunogenicity is a measure of the immune response to a therapeutic drug (e.g. a monoclonal antibody) resulting in generation of anti-drug antibodies. Clinical samples are tested in a sequence of binding anti-drug antibody (ADA) and neutralising antibody assays:

- a) Screening assay. Each sample is tested for the presence of anti-drug antibodies (ADA assay) and initially declared positive or negative according to assay cut-off criteria. Negative samples are not tested further. Positive samples are then tested in the confirmation ADA assay.
- b) Confirmation assay. Each positive sample from the screening assay is either confirmed positive in this assay (ADA assay), or is declared negative and are not tested further. Positive ADA samples are then tested in the titer assay and neutralization (NAb) assay.
- c) Titration assay. Each positive sample from the ADA confirmation assay is serially diluted to provide a titre, corresponding to the highest dilution factor that still yields a positive test result.
- d) Neutralising assay. Each positive sample from the ADA confirmation assay is tested with the neutralising antibody assay and found as either positive or negative in this assay (NAb assay).

The mepolizumab ADA (screening/confirmation/titration) assay version 2011N122789\_03 is performed at Alliance Pharma (method 120711M01.V02). The mepolizumab Nab assay version 2011N129752\_03 is being performed within GSK.

- A table will be produced summarising the number and percentage of negative and confirmed positive subjects ADA samples by visit in the AT population. The table will also summarise the highest assay result obtained post-baseline for each subject.
- A similar table will also be produced summarising results for the neutralising antibody assay in the AT Population, by visit.
- An additional summary of treatment emergent positive confirmatory binding antibody assay and results in the subset of subjects who did not have a positive confirmatory binding antibody assay result prior to the first dose of study treatment will also be presented.
- All immunogenicity results (i.e. ADA screening and confirmatory assay results, titre values and neutralising antibody results) will be listed.

The details of the planned Immunogenicity displays are presented in Appendix 10: List of Data Displays.

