### 11.10.6. Safety Tables

Safety:	Safety: Tables							
No.	Population	IDSL / Example Shell	Title	Programming Notes	Deliverable			
Exposu	re							
2.1.	AT	SHELL	Summary of Exposure to Study Medication	ICH E3 See format of Study Population Table 1.28 (200862 'final' reporting effort).	SAC			
2.2.	AT	SHELL	Summary of Exposure to Study Medication (Therapeutic Coverage) From Studies MEA115588, MEA115575, MEA115661 and 201312	See format of Study Population Table 7.74 (MEA115661 'manuscript1' reporting effort).	SAC			
Advers	e Events (AEs)							
2.3.	AT	SHELL	Overview of Adverse Events		SAC			
2.4.	AT	AE1	Summary of On-Treatment Adverse Events by System Organ Class and Preferred Term	ICH E3	SAC			
2.5.	AT	SHELL	Summary of Exposure Adjusted On-Treatment Adverse Events by System Organ Class and Preferred Term		SAC			

Safety:	Safety: Tables							
No.	Population	IDSL / Example Shell	Title	Programming Notes	Deliverable			
2.6.	AT	AE5	Summary of On-Treatment Adverse Events by Maximum Intensity by System Organ Class and Preferred Term	ICH E3 Add a Total column across all severities	SAC			
2.7.	AT	AE1	Summary of Post-Treatment Adverse Events by System Organ Class and Preferred Term		SAC			
2.8.	AT	AE5	Summary of Post-Treatment Adverse Events by Maximum Intensity by System Organ Class and Preferred Term	ICH E3 Add a Total column across all severities	SAC			
2.9.	AT	AE3	Summary of Common (>=3%) On-Treatment Adverse Events by Overall Frequency	ICH E3 ≥3% (prior to rounding to nearest percent)	SAC			
2.10.	AT	SHELL	Summary of Exposure Adjusted On-Treatment Common (>=3%) Adverse Events by System Organ Class and Preferred Term	≥3% (prior to rounding to nearest percent)	SAC			
2.11.	AT	AE1	Summary of On-Treatment Drug-Related Adverse Events by System Organ Class and Preferred Term	ICH E3	SAC			
2.12.	AT	SHELL	Summary of Exposure Adjusted On-Treatment Drug-Related Adverse Events by System Organ Class and Preferred Term		SAC			
2.13.	AT	AE5	Summary of On-Treatment Drug-Related Adverse Events by System Organ Class and Preferred Term and Maximum Intensity	Add a Total column across all severities	SAC			
2.14.	AT	AE1	Summary of Adverse Events Reported on Day of Dosing by System Organ Class and Preferred Term		SAC			
2.15.	AT	SHELL	Summary of On-Treatment Adverse Events by Age Group (12- 17, 18-64, >=65 years)		SAC			
2.16.	AT	SHELL	Summary of On-Treatment Adverse Events by Highest Anti Drug Antibody Result At Any Time Post Baseline		SAC			

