2.17.	AT	SHELL	Summary of Post-Treatment Adverse Events by Highest Anti Drug Antibody Result At Any Time Post Baseline		SAC			

Safety: Tables							
No.	Population	IDSL / Example Shell	Title	Programming Notes	Deliverable		
2.18.	AT	AE15	Summary of Common (>=3%) Non-serious Adverse Events by System Organ Class and Preferred Term (Number of Subjects and Occurrences)	FDAAA, EudraCT ≥3% (prior to rounding to nearest percent)	SAC		
Serious	and Other Sig	nificant Adverse	Events				
2.19.	AT	AE1	Summary of Pre-Treatment Serious Adverse Events by System Organ Class and Preferred Term		SAC		
2.20.	AT	AE1	Summary of On-Treatment Serious Adverse Events by System Organ Class and Preferred Term		SAC		
2.21.	AT	AE1	Summary of Post-Treatment Serious Adverse Events by System Organ Class and Preferred Term		SAC		
2.22.	AT	SHELL	Summary of Exposure Adjusted On-Treatment Serious Adverse Events by System Organ Class and Preferred Term		SAC		
2.23.	AT	SHELL	Summary of On-Treatment Serious Adverse Events by Age Group (12-17, 18-64, >=65 years)		SAC		
2.24.	AT	AE1	Summary of Fatal Serious Adverse Events		SAC		
2.25.	AT	SHELL	Summary of Fatal Serious Adverse Events by Age Group (12- 17, 18-64, >=65 years)		SAC		
2.26.	AT	AE1	Summary of Non-Fatal Serious On-Treatment Adverse Events by System Organ Class and Preferred Term		SAC		
2.27.	AT	AE1	Summary of Non-Fatal Serious Post-Treatment Adverse Events by System Organ Class and Preferred Term		SAC		
2.28.	AT	SHELL	Summary of Exposure Adjusted On-Treatment Non-Fatal Serious Adverse Events by System Organ Class and Preferred Term		SAC		

Safety:	Safety: Tables							
No.	Population	IDSL / Example Shell	Title	Programming Notes	Deliverable			
2.29.	AT	AE1	Summary of Drug-Related Fatal Serious Adverse Events by System Organ Class and Preferred Term		SAC			
2.30.	AT	AE5	Summary of Drug-Related Serious Adverse Events by System Organ Class and Preferred Term and Maximum Intensity	Add a Total column across all severities	SAC			
2.31.	AT	AE3	Summary of Adverse Events Leading to Permanent Discontinuation of Study Treatment or Withdrawal from Study by System Organ Class and Preferred Term /by Overall Frequency	IDSL	SAC			
2.32.	AT	SHELL	Summary of Exposure Adjusted On-Treatment Adverse Events Leading to Permanent Discontinuation of Study Treatment or Withdrawal from Study by System Organ Class and Preferred Term		SAC			

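### AE Table 2.16 groups subjects by highest post-baseline ADA result with no stated exposure adjustment, so unequal follow-up alone can make ADA-positive subjects look worse

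*SAP*

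**What the plan says.** SAP 11.10.6 lists Table 2.16 as "Summary of On-Treatment Adverse Events by Highest Anti Drug Antibody Result At Any Time Post Baseline". It is a non-standard shell with no programming note, and SAP Appendix 11 says that shells are available on request.

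The grouping variable is a maximum over all post-baseline samples. For the ADA results table, SAP 7.5.1 says: "The table will also summarise the highest assay result obtained post-baseline for each subject". The Protocol Summary (Study Design) sets ADA samples at "baseline (Visit 1), Weeks 48, 96, 144 and at the Exit Visit/Early Withdrawal Visit".

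SAP 7.2 says of AEs in general: "Exposure adjusted rates of AEs will also be presented to account for the length of exposure within the trial". In the display list, exposure-adjusted tables carry those words in their titles, for example "Summary of Exposure Adjusted On-Treatment Adverse Events by System Organ Class and Preferred Term". Six AE tables do so (2.5, 2.10, 2.12, 2.22, 2.28 and 2.32), and none is by ADA.

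Follow-up can last up to 172 weeks and ends country by country as the product becomes available (Protocol 3.1). SAP 11.6.1 expects no completers. The study has no hypotheses (SAP 2.4).

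**The concern.** Whether a subject counts as ADA-positive depends partly on how many samples were taken, and that depends on how long the subject stayed. Time in study also sets the chance of having an AE. A crude percentage by ADA group therefore mixes any antibody effect with length of follow-up.

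Protocol 1.3.1 lists immunogenicity as a risk because antibodies might produce adverse reactions. A table of AEs by ADA result will be read as evidence on that risk even though nothing is tested. An excess due only to longer follow-up could be taken for a signal. For some kinds of AE, a real signal could be hidden.

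**Working it through.** The documents state no ADA rate, AE rate or follow-up distribution, so there is no figure to reproduce. The check asks what the table would show if antibodies had no effect.

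**Inputs from the documents.** Post-baseline samples at Weeks 48, 96, 144 and Exit; maximum follow-up 172 weeks; about 375 subjects (Protocol 4.1); 365.25 days per year (SAP 11.5.4), i.e. 52.18 weeks.

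**Assumptions.** Each sample is positive with probability p = 1–3%, independently of AEs. A given AE occurs at λ = 0.15 per year. Follow-up T is uniform over a stated range.

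**Formulas.** With n(T) samples (1 up to Week 48, then 2, 3 and 4 after Weeks 48, 96 and 144), P(ADA+ | T) = 1 − (1 − p)^n and P(at least one AE | T) = 1 − exp(−λT/52.18).

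**Worked case: T uniform over 24–172 weeks, p = 2%.**

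| Follow-up (weeks) | Share of subjects | Mean T | n | P(ADA+) | P(AE) |
|---|---|---|---|---|---|
| 24–48 | 0.162 | 36 | 1 | 0.0200 | 0.098 |
| 48–96 | 0.324 | 72 | 2 | 0.0396 | 0.186 |
| 96–144 | 0.324 | 120 | 3 | 0.0588 | 0.291 |
| 144–172 | 0.189 | 158 | 4 | 0.0776 | 0.365 |

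- P(ADA+) = 0.162×0.0200 + 0.324×0.0396 + 0.324×0.0588 + 0.189×0.0776 = 0.0498.
- Mean follow-up is 113.4 weeks in ADA-positive and 97.2 in ADA-negative subjects (ratio 1.17).
- Subjects with the AE: 27.3% versus 23.8%, ratio 1.15.
- Events per 1000 subject-years: 150 in both groups, because expected events are λT and the divisor is T.

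**Other follow-up patterns (p = 2%).**

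| Follow-up (weeks) | Mean T, ADA+ / ADA− | % with AE, ADA+ / ADA− | Ratio | ADA+ among 375 | Excess subjects |
|---|---|---|---|---|---|
| 4–172 | 108.3 / 87.0 | 26.1 / 21.4 | 1.22 | 17.4 | 0.8 |
| 24–172 | 113.4 / 97.2 | 27.3 / 23.8 | 1.15 | 18.7 | 0.7 |
| 52–172 | 120.4 / 111.5 | 28.9 / 27.1 | 1.07 | 21.1 | 0.4 |
| 104–172 | 140.3 / 137.8 | 33.1 / 32.6 | 1.015 | 25.0 | 0.1 |
| all 172 | 172 / 172 | 39.0 / 39.0 | 1.00 | 29.1 | 0 |

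Moving p between 1% and 3% changes these ratios by less than 0.01. If positivity was carried in and persists, P(ADA+) no longer depends on T and the ratio is 1.00. The ratio also falls for common AEs: over 24–172 weeks at p = 2% it is 1.13 at 0.3 per year (46.5% versus 41.1%) and 1.02 at 3 per year (98.5% versus 97.0%).

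**Is time before the first positive sample the cause?** With everyone followed for 172 weeks and p = 2%, ADA-positive subjects contribute 0.0776 × 172 = 13.35 weeks per enrolled subject. Of these, 0.02 × (124 + 0.98×76 + 0.9604×28) = 4.51 weeks follow the first positive sample, so 66% precede it. The ratio is nevertheless exactly 1.00. Unequal exposure is what produces the excess.

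**AEs that end follow-up.** Such an event cuts off later samples. By simulation at 0.02 and 0.05 per year, with 5% positivity per sample or persistent seroconversion at 0.03 per year, the ADA+/ADA− ratio is 0.49–0.70 for percentages and 0.48–0.58 for rates per subject-year. For example, with 172 weeks planned for all, 5% per sample and 0.05 per year, it is 9.6% versus 16.4%. Dividing by exposure does not remove this. Splitting each subject's time at the first positive sample does, giving about 50 per 1000 subject-years in both states at a true rate of 0.05 per year.

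**The case against.** **The content of Table 2.16 cannot be seen.** That it is unadjusted is inferred from its title, and SAP 7.2 promises exposure-adjusted rates in general. The inference is reasonable because the SAP labels such tables consistently, but it remains an inference.

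**The size is uncertain and may be trivial.** The 1.22 ratio needs follow-up uniform over 4–172 weeks, which has 44/168 = 26% leaving before Week 48 and 116/168 = 69% before Week 120. Nothing in the documents supports that shape, and treatment was extended because some subjects would complete 120 weeks before the product was available. Over 104–172 weeks the ratio is about 1.015. In every pattern tabulated the excess is under one subject among the ADA-positive. This stands, and it limits the importance of the point.

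**Other displays exist.** Listing 49 gives each subject's antibody results, Listing 10 gives all AEs, and Listings 17–20 give anaphylaxis, systemic and local reactions. With few ADA-positive subjects, these can be read case by case. So Table 2.16 is not the only view of the question.

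**Other tables do not share the problem.** A reader might extend the point to Table 2.17, "Summary of Post-Treatment Adverse Events by Highest Anti Drug Antibody Result At Any Time Post Baseline". The last ADA sample is planned at Exit, four weeks after the last dose, where the on-treatment phase ends, so status is normally settled before those events. The SAP's exposure formula also counts on-treatment days, the wrong divisor there. A reader might likewise add the by-age tables, such as "Summary of On-Treatment Adverse Events by Age Group". Age is fixed at Visit 1, and nothing in the documents shows that follow-up differs by age.

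**Conclusion.** The point holds for Table 2.16 as a modest, inexpensive improvement. Grouping by a maximum over a variable number of samples, with unequal follow-up and no stated adjustment, can raise the crude AE percentage in ADA-positive subjects when there is no association. Under the assumed inputs the ratio runs from about 1.015 to 1.22 according to how widely follow-up is spread.

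Two stronger readings are tempting. One is that ADA-positive subjects will show more AEs regardless. The documents do not support this: the excess vanishes with equal follow-up or carried-in positivity, nearly vanishes for very common AEs, and reverses for AEs that end follow-up. Protocol 1.1 says that every subject enters with at least 12 months of treatment, so some carried-in positivity is plausible, though its share is not given. The other is that immortal time causes the excess. The equal-follow-up case rules that out; time before positivity matters only for AEs that end follow-up, and there it favours the ADA-positive group.

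The conclusion rests on the table being unadjusted, as its title suggests, and on assumed ADA and AE rates.

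**What to change.** In Table 2.16, show subject-years and events per 1000 subject-years for each ADA group beside the counts, using the existing formula in SAP 11.5.4. This removes the exposure effect for AEs that do not end follow-up.

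As a supporting display, classify AEs and person-time by ADA status at onset, starting from the Visit 1 sample. Starting at the first post-baseline sample instead would count subjects already positive at Visit 1 as negative for up to 48 weeks or longer. Show baseline-positive and treatment-emergent subjects separately; SAP 7.5.1 already isolates the "subset of subjects who did not have a positive confirmatory binding antibody assay result prior to the first dose of study treatment" for the ADA results. State where subjects with no post-baseline sample are placed.

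The cost is programming only. The drawback is imprecision. For follow-up over 24–172 weeks, the mean time beyond Weeks 48, 96 and 144 is 51.95, 19.51 and 2.65 weeks. ADA-positive time per enrolled subject is then p × [51.95 + (1−p)×19.51 + (1−p)²×2.65], which is 0.74 weeks at p = 1% and 2.20 at 3%. For 375 subjects that is 375 × 0.74/52.18 = 5 to 375 × 2.20/52.18 = 16 subject-years, before any baseline-positive subjects. With samples about 48 weeks apart, some AEs after true seroconversion will still be counted as ADA-negative, and a first positive at Exit adds almost no ADA-positive time.

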### 11.10.7. Safety Figures

Safety: Figures									
No.	Population	IDSL / Example Shell	Title	Programming Notes	Deliverable [Priority]				
Laborat	Laboratory								
2.1.	AT	LIVER14	Scatter Plot of Maximum Post-Baseline vs. Baseline for ALT	IDSL	SAC				
2.2.	AT	LIVER9	Scatter Plot of Maximum Post-Baseline ALT vs. Maximum Post- Baseline Total Bilirubin	IDSL	SAC				

### 11.10.8. Efficacy Tables

Efficac	Efficacy: Tables						
No.	Population	IDSL / Example Shell	Title	Programming Notes	Deliverable [Priority]		
Exacer	bations						
3.1	AT	SHELL	Overview of All Exacerbations	See Efficacy Table 2.61 (200862 'final' reporting effort)	SAC		
3.2	AT	SHELL	Summary of Frequency of All Exacerbations	See Efficacy Table 2.62 (200862 'final' reporting effort)	SAC		
3.3	AT	SHELL	Annualised Rate of Exacerbations	See Efficacy Table 2.64 (200862 'final' reporting effort)	SAC		
3.4	AT	SHELL	Overview of Exacerbation Rate by Treatment Allocated Within MEA115588 and Study Period (MEA115588, MEA115661 and 201312 combined)	See Efficacy Table 6.15 (MEA115661 'final' reporting effort)	SAC		
3.5	AT	SHELL	Analysis of Time to First Exacerbation	See Efficacy Table 2.68 (200862 'final' reporting effort)	SAC		
3.6	AT	SHELL	Summary of Frequency of Exacerbations Requiring Hospitalisation or Emergency Department visits	See Efficacy Table 2.62 (200862 'final' reporting effort)	SAC		
3.7	AT	SHELL	Annualised Rate of Exacerbations Requiring Hospitalisation or Emergency Department visits	See Efficacy Table 2.64 (200862 'final' reporting effort)	SAC		
3.8	AT	SHELL	Summary of Frequency of Exacerbations Requiring Hospitalisation	See Efficacy Table 2.62 (200862 'final' reporting effort)	SAC		
3.9	AT	SHELL	Annualised Rate of Exacerbations Requiring Hospitalisation	See Efficacy Table 2.64 (200862 'final' reporting effort)	SAC		
Asthma	a Control Quest	tionnaire (ACQ-5)					
3.10	AT	SHELL	Summary of Asthma Control Questionnaire (ACQ-5) Score	See Efficacy Table 2.34 (200862 'final' reporting effort)	SAC		

201312

Efficacy: Tables								
No.	Population	IDSL / Example Shell	Title	Programming Notes	Deliverable [Priority]			
Pre – B	ronchodilator I	EV1						
3.11	AT	SHELL	Summary of Clinic Pre-Bronchodilator FEV1 (mL)	See Efficacy Table 2.27 (200862 'final' reporting effort)	SAC			
Oral Co	Oral Corticosteroid Use							
3.12	AT	SHELL	Summary of OCS Dose (mg/day) During Each Reporting Period by Treatment Allocated Within MEA115575 and Study Period (MEA115588, MEA115661 and 201312 combined)	See Efficacy Table 6.16 (MEA115661 'final' reporting effort)	SAC			

### 11.10.9. Efficacy Figures

Efficacy: Figures							
No.         Population         IDSL / Example Shell         Title         Deliveral [Priority]							
Exacerbations							
3.1	AT	SHELL	Kaplan-Meier Cumulative Incidence Curve for Time to First Exacerbation	See Efficacy Figure 2.15 (200862 'final' reporting effort)	SAC		

### 11.10.10. Pharmacodynamic Tables

Pharmacodynamic: Tables							
No.	No.         Population         IDSL / Example Shell         Title         Programming Notes         Deliveration						
Blood Eosinophils							
4.1.	AT	SHELL	Summary of Blood Eosinophils (10  /L)	See Efficacy Table 2.73 (200862 'final' reporting effort), but exclude 'Placebo' column	SAC		

### 11.10.11. ICH Listings

ICH: Lis	ICH: Listings						
No.	Population	IDSL / Example Shell	Title	Programming Notes	Deliverable [Priority]		
Subject	Disposition						
1.	ASE	ES7	Listing of Reasons for Screen Failure	Journal Guidelines	SAC		
2.	ASE	IE3	Listing of Failed Inclusion/Exclusion criteria	ICH E3	SAC		
3.	AT	ES2	Listing of Reasons for Study Withdrawal	ICH E3	SAC		
4.	AT	SHELL	Listing of Current and Previous Treatment		SAC		
Demog	raphics						
5.	AT	DM2	Listing of Demographic Characteristics	ICH E3	SAC		
6.	AT	DM9	Listing of Race	ICH E3	SAC		
Medica	Medication Use						
7.	AT	CM6	Relationship Between ATC Level 1, Ingredient and Verbatim Text		SAC		
Protoco	Deviations			·	•		
8.	AT	DV2	Listing of Important Protocol Deviations	ICH E3	SAC		
Exposu	Exposure and Treatment Compliance						
9.	AT	EX3	Listing of Exposure Data	ICH E3	SAC		
Adverse Events							
10.	ASE	AE8	Listing of All Adverse Events	ICH E3	SAC		
11.	ASE	AE7	Listing of Subject Numbers for Individual Adverse Events	ICH E3	SAC		
12.	ASE	AE2	Listing of Relationship Between Adverse Event System Organ Classes, Preferred Terms, and Verbatim Text	IDSL	SAC		

ICH: Lis	ICH: Listings						
No.	Population	IDSL / Example Shell	Title	Programming Notes	Deliverable [Priority]		
Serious	s and Other Sig	nificant Adverse	Events				
13.	ASE	AE8	Listing of Fatal Serious Adverse Events	ICH E3	SAC		
14.	ASE	AE8	Listing of Non-Fatal Serious Adverse Events	ICH E3	SAC		
15.	ASE	AE14	Listing of Reasons for Considering as a Serious Adverse Event	ICH E3	SAC		
16.	AT	AE8	Listing of Adverse Events Leading to Withdrawal from Study / Permanent Discontinuation of Study Treatment	ICH E3	SAC		
Advers	e Events of Sp	ecial Interest					
17.	AT	SHELL	Listing of Adverse Events Meeting Anaphylaxis Criteria	See format of Safety Listing 7.10 (MEA115588 'final' reporting effort) Insert footnote: "Events displayed are a subset of reactions defined by the Investigator as being systemic"	SAC		
18.	AT	SHELL	Listing of Adverse Events Defined by the Investigator as a Systemic (non-allergic or allergic/hypersensitivity) Reaction	See format of Safety Listing 7.07 (MEA115588 'final' reporting effort). Also add a column stating whether AE is related to IP.	SAC		
19.	AT	SHELL	Listing of All Adverse Events Experienced by Subjects with at least one Adverse Event Defined by the Investigator as a Systemic (non-allergic or allergic/hypersensitivity) Reaction		SAC		
20.	AT	SHELL	Listing of Adverse Events Defined by the Investigator as a Local Injection Site Reaction	See format of Safety Listing 7.09 (MEA115588 'final' reporting effort). Also add a column stating whether AE is related to IP.	SAC		
21.	AT	SHELL	Listing of Opportunistic Infections	See format of Safety Listing 7.10 (MEA115588 'final' reporting effort)	SAC		

CONFIDENTIAL

201312

ICH: Lis	ICH: Listings							
No.	Population	IDSL / Example Shell	Title	Programming Notes	Deliverable [Priority]			
22.	AT	SHELL	Listing of Malignancies	See format of Safety Listing 2.03 (mid_mepo_iss 'iss_nda' reporting effort)	SAC			
23.	AT	SHELL	Listing of Serious Cardiac, Vascular and Thromboembolic (CVT) Adverse Events	See format of Safety Listing 7.10 (MEA115588 'final' reporting effort)	SAC			
24.	AT	SHELL	Listing of Serious Ischemic Adverse Events	See format of Safety Listing 7.10 (MEA115588 'final' reporting effort)	SAC			
Cardio	vascular Event	s						
25.	AT	SHELL	Listing of Investigator Reported Cardiovascular Events: Arrhythmias	See format of Safety Listing 7.11 (MEA115588 'final' reporting effort)	SAC			
26.	AT	SHELL	Listing of Investigator Reported Cardiovascular Events: Congestive Heart Failure	See format of Safety Listing 7.12 (MEA115588 'final' reporting effort)	SAC			
27.	AT	SHELL	Listing of Investigator Reported Cardiovascular Events: Cerebrovascular Events/Stroke	See format of Safety Listing 7.13 (MEA115588 'final' reporting effort)	SAC			
28.	AT	SHELL	Listing of Investigator Reported Cardiovascular Events: Deep venous Thrombosis/Pulmonary Embolism	See format of Safety Listing 7.14 (MEA115588 'final' reporting effort)	SAC			
29.	AT	SHELL	Listing of Investigator Reported Cardiovascular Events: Myocardial Infarction/Unstable Angina	See format of Safety Listing 7.15 (MEA115588 'final' reporting effort)	SAC			
30.	AT	SHELL	Listing of Investigator Reported Cardiovascular Events: Peripheral Arterial Thrombosis Embolism	See format of Safety Listing 7.16 (MEA115588 'final' reporting effort)	SAC			
31.	AT	SHELL	Listing of Investigator Reported Cardiovascular Events: Pulmonary Hypertension	See format of Safety Listing 7.17 (MEA115588 'final' reporting effort)	SAC			
32.	AT	SHELL	Listing of Investigator Reported Cardiovascular Events: Revascularisation	See format of Safety Listing 7.18 (MEA115588 'final' reporting effort)	SAC			
33.	AT	SHELL	Listing of Investigator Reported Cardiovascular Events: Valvulopathy	See format of Safety Listing 7.19 (MEA115588 'final' reporting effort)	SAC			

ICH: Listings								
No.	Population	IDSL / Example Shell	Title	Programming Notes	Deliverable [Priority]			
34.	AT	SHELL	Listing of Investigator Reported Cardiovascular Events: All Cause Deaths	See format of Safety Listing 7.20 (MEA115588 'final' reporting effort)	SAC			
35.	AT	SHELL	Listing of CEC Adjudicated Cardiovascular Events: Congestive Heart Failure	See format of Safety Listing 7.17 (MEA115666 'fina_01I' reporting effort)	SAC			
36.	AT	SHELL	Listing of CEC Adjudicated Cardiovascular Events: Cerebrovascular Events/Stroke	See format of Safety Listing 7.18 (MEA115666 'fina_01I' reporting effort)	SAC			
37.	AT	SHELL	Listing of CEC Adjudicated Cardiovascular Events: Deep venous Thrombosis/ Pulmonary Embolism	See format of Safety Listing 7.19 (MEA115666 'fina_01I' reporting effort)	SAC			
38.	AT	SHELL	Listing of CEC Adjudicated Cardiovascular Events: Myocardial Infarction /Unstable Angina	See format of Safety Listing 7.20 (MEA115666 'fina_01I' reporting effort)	SAC			
39.	AT	SHELL	Listing of CEC Adjudicated Cardiovascular Events: Peripheral Arterial Thrombosis Embolism	See format of Safety Listing 7.21 (MEA115666 'fina_01I' reporting effort)	SAC			
40.	AT	SHELL	Listing of CEC Adjudicated Events: All Cause Deaths	See format of Safety Listing 7.22 (MEA115666 'fina_01I' reporting effort)	SAC			
Hepato	Hepatobiliary (Liver)							
41.	AT	LIVER5	Listing of Liver Monitoring/Stopping Event Reporting		SAC			
42.	AT	LB5	Chemistry Results for Subjects Meeting Liver Monitoring/Stopping Event Criteria		SAC			
43.	AT	MH2	Listing of Medical Conditions for Subjects with Liver Stopping Events		SAC			

ICH: Listings							
No.	Population	IDSL / Example Shell	Title	Programming Notes	Deliverable [Priority]		
44.	AT	SU2	Listing of Substance Use for Subjects with Liver Stopping Events	See format of Safety Listing 7.22 (MEA112997 'final' reporting effort)	SAC		
45.	AT	LIVER13	Listing of Subjects Meeting Hepatobiliary Laboratory Criteria Post-Baseline		SAC		
46.	AT	SHELL	Mepolizumab Concentrations Following Onset of Liver Event		SAC		
All Lab	All Laboratory						
47.	AT	LB5	Listing of All Laboratory Data for Subjects with Any Value of Potential Clinical Importance	ICH E3	SAC		
ECG							
48.	AT	EG6	Listing of All ECG Findings for Subjects with an Abnormal ECG Interpretations	IDSL	SAC		
Immunogenicity							
49.	AT	SHELL	Listing of Immunogenicity Results	See format of Other Assessments Listing 8.01 (MEA115588 'final' reporting effort)	SAC		
Efficacy	Efficacy						
50.	AT	SHELL	Listing of Exacerbations	See format of Efficacy Listing 6.01 (MEA115588 'final' reporting effort)	SAC		

11.11.

